### **3.0 Outcome Measures/Endpoints**

#### **3.1 Primary Outcome Measures**

Outcomes of interest include recruitment, retention, adherence (i.e., exercise prescription and assessments), perceived exercise difficulty, and adverse event rates. Project success will be based on 83% [20 of 24] of randomized participants completing 8 weeks of exercise training.

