### 3.3 Tertiary/Exploratory/Correlative Outcome Measures

Tertiary outcome measures of interest include plasma concentrations of sICAM-1, s-VCAM-1, sNCAM, MPO, IFN $\gamma$ , IL-1 $\beta$ , BDNF, TNF- $\alpha$ , and IL-10 obtained from a venous blood sample taken at baseline and post-intervention.

Statistically significant decreases in endothelial microparticle concentrations from baseline to post-intervention in BR+EX that are above any decrease observed in EX will be considered a successful outcome.

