Based on participant responses to the questions, research personnel will determine preliminary eligibility for an on-site visit. If it appears the participant meets the preliminary eligibility, an on-site visit will be scheduled, and a consent form will be mailed / emailed to the participant for their consideration and review. After the study participant has had several days to review the consent form, research personnel will call the participant to answer any further questions regarding the consent form. Participants will be enrolled in small ( $n = 9$ ) cohorts or "waves" to facilitate social support and adherence to the supervised exercise training sessions. We anticipate having 9 waves to successfully reach our target  $n$ . This assumes that each wave will have 4 participants, hence, 4 participants x 9 waves = 36 total participants.

At the on-site screening visit, research personnel will once again cover inclusion/exclusion criteria, study procedures, requirements, and risks. Following written informed consent, participants will have their body weight and standing height measured to determine their body mass index (i.e., 25.0-39.9 kg/m^2). Current prescription drug use will be recorded by having

participants physically bring their prescription labels or medication bottles to the testing site. Additionally, participants will complete a Medical History Questionnaire (see attachments).

Written authorization will be obtained from consented participants to allow research personnel to contact the participant's primary care physician to receive physician's clearance prior to study testing visits. The physician will be asked to provide their assent or dissent for their patient to participate in the exercise testing protocols and supervised group exercise sessions involved with this study. They will have the option to indicate any modifications that may be necessary for the patient to participate safely. The Physician Clearance Form (see attachments) will be faxed to the patient's physician following the screening visit.

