Participants will perform baseline assessments (**Visits 1-2**) prior to randomization. Subsequently, participants will be randomly selected to: 1) control (EX only) or 2) BR+EX. Group allocation will be determined at random using a computer-based number generator in blocks of 2 to ensure equal between-group distribution (i.e.  $n = 2$  Ex only;  $n = 2$  BR+EX). Each number will be kept in a sealed envelope until completion of **Visits 1-2**.

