### **12.0 Statistical Considerations**

Rather than confirm efficacy, this proposal addresses elements of feasibility such that we intend to generate preliminary effect sizes for a larger-scale investigation. Descriptive statistics and calculation of rates (e.g., recruitment, retention, adherence, and adverse event) will be used for study aim 1. Between-group differences in descriptive data along with aims 2(a,b) and 3 will be evaluated using an unpaired t-test. Effect size calculations will be performed with Cohen's  $d$  to qualify substantive differences: small (0.2), medium (0.5), and large (0.8). Potential covariates of interest include age, body mass, body fat percentage, and/or markers of inflammation. Non-normally distributed data will be log-transformed. Two-tailed parametric correlations (Pearson) will be performed and based on consequent results, multiple linear regression will be used to examine changes in inflammation, endothelial function, distance in 6-minute walk test, leg strength, and resting blood pressure/arterial stiffness.

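### Section 12.0 lets Pearson correlations choose the multiple regressions in the same data, so the regressions' p-values, confidence intervals and R-squared are not valid at face value

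*Combined protocol and SAP*

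**What the plan says.** Section 12.0 sets the sequence. "Two-tailed parametric correlations (Pearson) will be performed", and then "based on consequent results, multiple linear regression will be used to examine changes in inflammation, endothelial function". The list of regression outcomes continues with "distance in 6-minute walk test, leg strength, and resting blood pressure/arterial stiffness", which makes five domains. Two sentences earlier the section says: "Potential covariates of interest include age, body mass, body fat percentage, and/or markers of inflammation".

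The section gives no significance level, rule for what counts as a result worth following up, limit on the number of predictors, multiplicity control or shrinkage. It does not say whether study arm is a term in the regressions, or whether covariates are baseline values only.

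The same section assigns Aims 2(a,b) and 3 to an unpaired t-test with Cohen's d, and presents the study as feasibility work rather than confirmation of efficacy. Nothing in it labels the regressions as hypothesis-generating.

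Two sample sizes appear. Section 3.1: "Project success will be based on 83% [20 of 24] of randomized participants completing 8 weeks of exercise training". Section 6.0: "4 participants x 9 waves = 36 total participants". Section 3.3 lists nine circulating markers, beginning "Tertiary outcome measures of interest include plasma concentrations of sICAM-1, s-VCAM-1, sNCAM, MPO".

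**The concern.** If a correlation has to look strong before a regression is run, the regression is fitted only where chance or truth has already produced a strong association. Its standard p-value and confidence interval assume the model was chosen without looking at the data, so they overstate the evidence. R-squared is inflated for the same reason.

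At stake is how the regressions are read. Chance associations could be reported as predictors of change in walk distance, endothelial function or arterial stiffness, and could then influence the larger study that this pilot is meant to inform.

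**Working it through.** **Inputs**

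- N: 20/24 = 83.3% and 4 × 9 = 36, so both of the plan's figures reproduce. N = 24 and 36 are used as the range, with n = 20 for completers only.
- Alpha and screen: not stated. Two-sided p<0.05 is assumed, with p<0.10 also tried.
- Candidates, k: not stated. Section 12.0 names four kinds. Counting all nine Section 3.3 markers gives 3 + 9 = 12. So k = 4 to 12 is an assumed range.
- Truth: no predictor is related to the outcome.

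The plan states no error rate for this step, so there is none to reproduce.

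**1. Passing the screen.** For independent predictors, P(at least one passes) = 1 − 0.95^k.

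- k = 4: 1 − 0.8145 = 18.5%
- k = 12: 1 − 0.5404 = 46.0%

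N does not enter this formula.

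**2. What the regression then adds.** If one predictor passes, the regression F equals r²(n−2)/(1−r²), which is the square of the correlation's t statistic. It is the same test, so the slope's 95% interval excludes zero by construction. In 6,000 simulated null data sets per setting (N = 24 and 36, independent predictors), a selected model held on average about 1.1 predictors (k = 4) or 1.3 (k = 12). Its F test was significant in 99.9% to 100% of runs in which anything was selected.

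| Setting | Overall F test significant |
|---|---|
| k = 4, independent, N = 24 / 36 | 19.0% / 18.4% |
| k = 12, independent, N = 24 / 36 | 45.9% / 45.9% |
| k = 4, predictors correlated 0.3, N = 24 / 36 | 16.7% / 17.5% |
| k = 12, predictors correlated 0.3, N = 24 / 36 | 39.4% / 40.1% |
| k = 12, independent, p<0.10 screen, N = 24 | 45.4% |
| Model fixed in advance | 5% |

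Across separate simulations, the independent-predictor figures are about 18% (k = 4) and 45% to 47% (k = 12).

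**3. R-squared.** The smallest r² that passes is t²/(n−2+t²), where t is the two-sided 5% critical value.

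| n | Smallest \|r\| passing | Smallest r² | Mean R² when selected | Mean adjusted R² when selected |
|---|---|---|---|---|
| 20 | 0.44 | 0.197 | 0.28–0.32 | 0.24–0.27 |
| 24 | 0.40 | 0.164 | 0.24–0.27 | 0.20–0.23 |
| 36 | 0.33 | 0.108 | 0.16–0.19 | 0.13–0.16 |

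The true value is 0 throughout. Adjusted R-squared does not repair a screened model, because it counts only the predictors that survived. For a model fixed in advance, adjusted R-squared averages 0 under the null, while raw R-squared averages p/(n−1) for p predictors. With p = 4 that is 4/23 = 0.17 at N = 24 and 4/35 = 0.11 at N = 36.

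**4. Any significant coefficient.** This rate is compared with a fixed, unscreened model holding the same candidates.

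| N | k | Screened | Fixed |
|---|---|---|---|
| 24 | 4 / 8 / 12 | 18% / 31% / 44% | 17% / 28% / 33% |
| 36 | 4 / 8 / 12 | 17% / 32% / 43% | 17% / 29% / 39% |

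Most of this rate comes from the number of candidates. The error particular to screening shows in the overall F test (step 2).

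**5. The other reading.** The correlations might decide which outcomes are modelled rather than which predictors enter. That is also data-driven. With 4 candidates and 5 outcome domains there are 20 pairs, and if they were independent, the chance that at least one passes is 1 − 0.95^20 = 64.2%.

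**The case against.** The strongest reply has four parts.

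- **The rule is inferred.** Section 12.0 never says that predictors passing a p-value threshold enter the model, and the covariate sentence is separate from the correlation sentence. This stands as to the exact mechanism, so the percentages are illustrative. It does not remove the point: the text makes the regressions depend on the correlation results, whether that dependence chooses predictors or outcomes.
- **The error is mostly multiplicity.** A reader might infer that the 17% to 44% chance of some significant coefficient is caused by screening in a small trial. Step 4 does not support that. A fixed model with as many candidates comes close, and the rate hardly changes with N. The F test is where screening does its own damage.
- **The R-squared figures are conditional.** They average only over trials in which something was selected. Over all null trials, counting 0 when nothing passes, the mean is 0.04 to 0.12 at N = 24, and a fixed 12-predictor model has a higher raw mean (12/23 = 0.52). This is correct. But a reader sees R-squared only when a model is reported, and in the fixed model adjusted R-squared averages 0, against 0.20 to 0.23 after screening.
- **The stakes are modest.** The regressions are supplementary, and the preliminary effect sizes come from Cohen's d. This stands and limits the point.

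One more inference goes too far: that the models will adjust for an effect of the intervention, because inflammation markers are both candidate covariates and Aim 3 outcomes. The plan does not say that post-baseline values will be covariates, or that arm is a term. It only fails to exclude this.

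**Conclusion.** The point holds for the regressions in Section 12.0. Choosing them from correlations in the same data makes their p-values, confidence intervals and R-squared invalid at face value. Steps 2 and 3 give the size, which rests on an assumed alpha of 0.05, an assumed p<0.05 screen and 4 to 12 candidates with no true association. The direction held in every setting tried. The false-positive rate is driven by the number of candidates; the small sample drives the R-squared inflation.

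Two stronger conclusions are not supported. Twelve candidates is not the plan's count: Section 12.0 does not say which markers count as inflammation markers, and Section 3.3 refers to the nine as endothelial microparticles. Nor are the trial's main results compromised: the Section 3.1 feasibility criterion, the unpaired t-tests and Cohen's d for Aims 2 and 3 do not pass through this step. The matter is worth correcting, but it is not a fault in the primary analysis.

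**What to change.** In Section 12.0:

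1. Delete the clause that makes the regressions depend on the correlation results.
2. Name the variable that represents each outcome domain, and pre-specify one model for it: post-intervention value on arm, the baseline value of that outcome, and at most one or two named covariates such as age and body fat percentage, all covariates measured at baseline.
3. Report adjusted R-squared, because raw R-squared stays inflated in small samples even for a fixed model. Interpret the individual coefficients with their confidence intervals; the overall F test says little here, since the baseline value can be expected to predict the follow-up value.
4. Report all Pearson correlations with confidence intervals, label them hypothesis-generating, and do not use them to choose models.

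The cost is a wording change. The downside is less freedom to explore predictors of change within the models, since the fixed model asks mainly about the effect of arm. That exploration is kept, in descriptive form, by item 4.

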### **13.0 Statistical Data Management**

Primary data will be collected via paper and digital instruments and stored electronically on password protected/network secure university servers. The storage location will be backed up automatically every day. Quality assurance steps will include: 1) built in range checks using physiologically relevant values and 2) periodic means testing. The following quality control methods will be used: data entry will be performed by two study personnel and will be periodically range checked and means tested to check for data entry errors.

### **14.0 Privacy/Confidentiality Issues**

All outlined procedures will be performed in private laboratory settings and medical facilities to respect the participants' right to privacy. Only approved members of the research team (listed on IRB personnel tab) will be present during procedures. While there is not absolute guarantee of confidentiality, every practical precaution will be taken.

Each study participant will be assigned a unique ID. Samples (including blood collection vials) and collected data will be de-identified using this unique ID. Information containing identifying data (e.g. Informed Consent Statements, Physician Clearance Forms) will be stored separately from de-identified data. All data will be stored either electronically on computers in locked rooms or in password protected files on department servers (OnCore, BoxHealth Account), or as paper copies stored in locked rooms within separately locked filing cabinets.

### **15.0 Follow-up and Record Retention**

Study recruitment will be ongoing. The entire study is expected to last a duration of 24 months.

It is our intention to retain data collected indefinitely. Paper copies of study documents will be stored in locked rooms within separately locked filing cabinets separate from any identifying documents (e.g. Informed Consent Statements, Physician Clearance Forms). All electronic data will be stored on password-protected department servers (OnCore, BoxHealth Account) that are backed up daily. If recorded data are eventually deleted, paper copies will be shredded appropriately, all code keys deleted containing identifiable information, and remaining data permanently deleted from computers and portable storage mediums.

## 17.0 Appendix

All supplemental materials have been uploaded to the protocol attachments section for Questionnaire (A+B), Participant Adverse Event Reporting Form, Recruitment Flyers, Participant Instruction Sheet, and Participant Dietary Recall Instruction Sheet.
